5.8.4.4 Setting

Three groups will be defined as NHS sites, charity sites and school sites. No definitive prediction has been made for this subgroup analysis. We note that schools and charities have a greater diversity in terms of the kinds of practitioner and their levels of qualifications. Participants randomised within a school setting may be more comfortable in receiving the intervention as it is an environment they are familiar with. Therefore, it could be suggested that participants belonging to NHS or school sites may benefit more compared with charity sites.

5.8.4.5 Ethnicity

Two groups will be defined as white and non-white ethnicity. We predict that those from minority ethnic groups may do less well as the intervention may be more culturally removed for this group than for the white ethnicity group.

5.9 Analysis of Secondary Outcomes

All secondary outcomes will be reported descriptively at each collected time point by trial arm. This section provides details of the planned analyses for each secondary outcome. All secondary analyses will follow the same model selection process and missing data assumptions as the primary model.

5.9.1 RCADS-25 Grouped T-Scores

The continuous RCADS-25 T-score will be categorised into three groups as defined by the clinical cut-offs stated in section 5.2.1. This analysis will compare the odds ratio at 6- and 12-

months post randomisation of being in a higher category than the non-clinical range, which will act as the reference category. This will be analysed using a mixed ordinal logistic regression model, with the interpretation of one unit increase in the response variable, this would correspond to being within the next category level. The model will adjust for the same fixed and random effects as the primary model. The proportional odds assumption for ordinal regression models will be assessed using the Brant test.

5.9.2 CDRS-R

The CDRS-R will be analysed first using the T-scores as a continuous measure and second as an ordered categorical measure.

The continuous CDRS-R T-scores will be used as the response variable. This analysis will compare the adjusted mean difference of the CDRS-R score between treatment arms at both 6- and 12-months post randomisation. A linear mixed effects regression model will be used, replacing the baseline value of RCADS-25 T-Score to that of the baseline CDRS-R T-score, with all other fixed and random covariates remaining the same as the primary model.

For the second analysis, the CDRS-R T-scores will be categorised into three groups as defined in section 5.2.3. This analysis will compare the odds of being in a higher category than the non-diagnosable depression category for each treatment arm. A mixed ordinal logistic regression model will be used, replacing the baseline value of RCADS-25 T-Score to that of the baseline CDRS-R T-score, with all other fixed and random covariates remaining the same as the primary model. This will be analysed at both 6- and 12-months post randomisation. The proportional odds assumption for ordinal regression models will be assessed using the Brant test.

5.9.2.1 Sensitivity analysis for non-visual appointments

A sensitivity analysis will be conducted including the participant's CDRS-R T-scores that were unable to complete Items 15 or 17 due to being a telephone or online (with no camera) appointment. The secondary CDRS-R analysis models (described above in section 5.9.2) will be rerun but including the participants that had these types of appointments.

5.9.3 BADS-SF

The total score of the BADS-SF questionnaire will be used as the continuous response variable for this secondary analysis. This analysis will compare the adjusted mean difference of the BADS-SF score between treatment arms at both 6- and 12-months post randomisation. A linear mixed effects regression model will be used, replacing the baseline value of RCADS-25 T-Score to that of the baseline BADS-SF score, with all other fixed and random covariates remaining the same as the primary model.

5.9.4 Adverse Events

Adverse events (AEs) and Serious Adverse Events (SAEs) will be summarised descriptively, by trial arm, and overall. The number of AEs and SAEs per participant will be presented, by treatment group and overall. The event type, expectedness, and relatedness to the study treatment of the AEs and SAEs will be summarised similarly.

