3.3 Interventions

3.3.1 Behavioural activation

A bespoke, standardised BA package was developed which was inspired and informed by published literature, public and patient involvement (PPI) activities and a feasibility study.

The BA sessions with a professional will guide and support each young person to identify, schedule, complete and monitor pleasures, necessities and goals in day-to-day life that connect with what and who is important to them. These may be things that the young person has stopped doing or doing less, which they can start doing again or more. There may be things that the young person would like to do or things that the young person never thought of doing for which they need help to start. There may be things that they have been doing routinely but no longer enjoy and need to change them in some way.

The young person will keep a diary in which they will make a note of each activity that they complete. Some of these activities will be scheduled and others will be unplanned, routine or spontaneous. The young person will score enjoyment, achievement and/or connection for each activity on a 0-10 scale (0=no enjoyment/achievement/connection, 10=great enjoyment/achievement/connection). Over the course of the week, activities that score high

on enjoyment, achievement and connection are highlighted and encouraged. Activities that score low can be reduced or changed so that they become more enjoyable or rewarding.

Activities that have not been completed can be postponed, cancelled, or changed – depending on the reasons for not being completed (the young person did not consider them important, or they were too difficult or other activities took priority). A graded and stepped approach to activities will help young people overcome obstacles such as hesitation and tiredness that are to be expected with depression. Some activities may actually make young people feel worse or may be harmful, destructive or counterproductive; these need to be identified and reduced/stopped.

The BA programme is organised in 5 “modules” which can be completed in up to 8 weekly sessions of 30-40 minutes each in a blended model of professional-guided sessions and self-directed activities. A 5-module approach has been used by McCauley et al (2016a) in their published guide (pp. 12-13). The content of these 5 modules is bespoke to ComBAT.

Table 1: The Five BA modules in ComBAT.

Module	Topics covered

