3.3.2 Usual care

Usual practice for child and adolescent mental health can be widely varied and inconsistent, as we have learnt from the mapping exercise, we carried out within our feasibility study and from our experiences of completing similar NIHR-funded studies, including ASPECT (Wright, et al., 2018), I-SOCIALISE (Varley et al., 2019), CCBT (Wright et al., 2017), Young SMILES (Gellatly et al, 2019). Usual care may be no intervention, signposting to alternative sources of support, general discussion, supportive counselling, relaxation, recreation groups, guided self-help or psychological therapies including CBT and IPT.

Professionals who are involved in usual care also vary greatly from one community setting to another: from assistants and support workers (e.g. family support workers, teaching assistants, emotional literacy support workers) to professionals who are trained in counselling, low intensity interventions (e.g. psychological wellbeing practitioners) and specialist high intensity interventions (e.g. CBT therapists, family therapists). This was reflected in our mapping exercise completed within our feasibility study where we also found much variation in the frequency, and both session number and length of support offered to young people with depression across services.

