3.4.3 Other Collected Data

- **Screening CRF**
 - PHQ-9A:
 - items 1-9
 - supplementary items 10-13 (risk questions)
 - total raw score
 - Date of screening
 - Inclusion criteria:
 - Aged between 12-18 years of age.
 - Scored at least 65 on the RCADS Depression Subscale.
 - Scored at most 14 on the PHQ-9A and did not answer risk questions in the affirmative (if scored greater than 14 – attends a secondary eligibility assessment with clinical member of the ComBAT team).
 - Exclusion criteria:
 - Young person eligible for secondary care CAMHS
- **Screening log**
 - Young person's initials (ID given if randomised)
 - Site name
 - Site ID
 - Name of location young person referred from:
 - Child and Adolescent Mental Health Services (CAMHS) name
 - Charity/Service name
 - School name
 - Referring professional
 - Research assistant
 - Date expression of interest received
 - Date of screening
 - RCADS Depression subscale score (as determined by screening CRF)
 - PHQ-9A score (as determined by screening CRF)
 - Young person eligible
 - Clinician follow-up call
 - Reason for screen failure/reason for ineligibility
 - Young person contacted for consent
 - Young person consented
 - Reason for non-consent
 - Additional notes

- **Baseline CRF**
 - Participant ID
 - Date completed
 - Date of birth
 - Gender
 - Ethnicity
 - Religion
 - Current living status
 - Living with parents, friends, alone, etc.
 - Number of people living in the same household
 - Number of people under 18 in the same household
 - Current education status
 - In education
 - Type of education
 - Employment status
 - Preference of support delivery
- **Therapist Demographic Information**
 - Therapist initials
 - Role (e.g. Child wellbeing practitioner, Nurse, Counsellor)
 - Grade
 - Organisation
 - Age (Grouped)
 - Gender
 - Time working with young people
 - Approaches used when supporting young people
- **Session record (behavioural activation)**
 - Participant ID
 - Date completed
 - Location of session (online, telephone, in person)
 - Professional's name
 - Session recorded
 - Adverse events
 - Anyone else present (parent, sibling etc.)
 - Type of session (assessment, intervention, or review)
 - Strategies used during the session
 - Time spent preparing the session (mins)
 - Length of session (mins)
 - Time spent on administration after the session (mins)
- **Session record (usual care)**
 - Participant ID
 - Date completed
 - Location of session (online, telephone, in person)

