 - Professional's name
 - Session recorded
 - Adverse events
 - Anyone else present (parent, sibling etc.)
 - Approach and support offered during the session
 - Strategies covered during the session
 - Time spent preparing the session (mins)
 - Length of session (mins)

- Time spent on administration after the session (mins)
- **Month 6 CRF**
 - Participant ID
 - Date completed
 - Aspects of care questionnaire (8-items)
- **Month 12 CRF**
 - Participant ID
 - Date completed
 - Aspects of care questionnaire (8-items)
- **Fidelity assessment**
 - Professional's name
 - Name of person assessing fidelity
 - Participant ID
 - Date of session
 - Session number
 - Professional's ability to deliver intervention (behavioural activation sessions only, 1-Limited, 2-Sufficient, 3-Excellent)
- **Change of Status**
 - Participant ID
 - Date completed
 - Date of birth
 - Pre-randomisation withdrawal
 - Post-randomisation withdrawal (treatment only, follow-up only, full withdrawal)
 - Reason for change in status
 - Date of death (if applicable)
 - Further information of change in status
 - Researchers name
 - Researchers signature
- **Unblinding**
 - Participant ID
 - Date of unblinding
 - Source of unblinding
 - Reason for unblinding
 - Method of unblinding
 - Additional details
- **Adverse events**
 - Participant ID
 - Date event reported
 - Event type (non-serious or serious AE)
 - Event reported by
 - Event reported to
 - Time point of adverse event
 - Date of onset of event
 - Description of event and how it was reported
 - Outcome of event (recovered/still ongoing)
 - Date recovered (if applicable)
 - Additional comments
 - Name of person reporting AE
 - Date report completed
 - Name of ComBAT team member reviewing the AE

- Date report reviewed
- **Serious adverse events**
 - Participant ID
 - Date event reported
 - Event reported by
 - Event reported to
 - Time point of adverse event
 - Date of onset of event
 - Description of event and how it was reported
 - Classification of SAE
 - CI Assessment-Expected SAE
 - Relationship to support received
 - Outcome of event (fully recovered / partially recovered / still ongoing / died)
 - Date fully recovered (if applicable)
 - Date partially recovered (if applicable)
 - Date of death (if applicable)
 - Name of person reporting SAE
 - Date report completed
 - Name of ComBAT team member reviewing the SAE
 - Date report reviewed
- **Adverse event follow-up**
 - Participant ID
 - Date initial event reported

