4.2.3 RCADS-25 Qualtrics questionnaire

At both 6 and 12 months, if the research team have been unable to make contact with a participant to arrange a follow-up appointment, a Qualtrics questionnaire containing only the primary outcome (RCADS 25 items) will be sent to the participant. This is to minimize any missing data of the primary outcome measure and ensure that we achieve 90% power as stated in section 3.5 above.

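### Pooled adverse-event counts by arm may reflect unequal ascertainment, because events can be recorded at sessions and the number of sessions may differ between arms

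*SAP*

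**What the plan says.** Section 5.9.4 has three sentences. Adverse events (AEs) and serious adverse events (SAEs) are described by arm and overall; "The number of AEs and SAEs per participant will be presented, by treatment group and overall"; and event type, expectedness and relatedness are summarised in the same way. There is no split by source or period and no caution about ascertainment. The template tables in section 8.1 contain no AE table, so these sentences are all that the SAP fixes about AE presentation.

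Other sections show where events can be recorded:

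- Section 3.4.3 lists "Adverse events" as a field on the session record of each arm.
- Section 3.3.1 gives BA as "up to 8 weekly sessions of 30-40 minutes each".
- Section 3.3.2 says "Usual care may be no intervention, signposting to alternative sources of support", but the same sentence goes on to supportive counselling, guided self-help, CBT and IPT. The section also reports much variation in session number.
- Section 3.7 sets follow-up at 6 and 12 months in both arms.
- Section 4.2.3 adds that, for participants who cannot be contacted, "a Qualtrics questionnaire containing only the primary outcome (RCADS 25 items) will be sent to the participant".
- The AE and SAE forms in section 3.4.3 record who reported the event, the "Time point of adverse event" and the date of onset.
- Section 5.6 summarises sessions attended by arm, without linking them to AEs.

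**The concern.** A count of recorded events is the product of how often events happen and how often someone is in a position to record them. If one arm is seen more often, it will tend to show more events even when the true rates are the same. Here the number of sessions is part of what differs between the arms, and section 5.9.4 adds session reports and all other reports into one count.

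Section 5.9.4 is the only safety summary in the SAP. As written, a reader could not tell from the AE summary itself how much of a difference between arms, or of an apparent absence of one, comes from contact frequency. The choice of split is best made before counts by arm are seen, since one chosen afterwards could look selective.

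**Working it through.** The SAP states no AE rate, no detection probability and no expected number of usual-care sessions, so it has no AE figure to reproduce. What follows is illustration. All probabilities are assumptions, and the true event rate is set equal in both arms.

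**1. Opportunities to record an event.** Opportunities = sessions + 2 follow-ups. BA is at its stated maximum of 8 sessions, giving 8 + 2 = 10. That AEs are asked about at follow-up is itself an inference: the Month 6 and Month 12 form lists in section 3.4.3 show no AE item.

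| Usual-care sessions (assumed) | Opportunities, BA v usual care | Ratio |
|---|---|---|
| 0 | 10 v 2 | 5.0 |
| 4 | 10 v 6 | 1.67 |
| 8 | 10 v 10 | 1.0 |
| 12 | 10 v 14 | 0.71 |

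**2. Recorded events.** Let pF be the chance that an event is recorded without any session, w the share of events with onset in the session period, 0.9 the chance that sessions pick up such an event, and q usual-care session coverage relative to BA. Then

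ratio BA : usual care = [pF + (1 − pF) × w × 0.9] / [pF + (1 − pF) × w × 0.9 × q].

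The range taken is pF from 0.3 to 0.8 and w from 8/52 = 0.15 (events spread evenly over 12 months, sessions filling 8 weeks) to 0.5.

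- Largest effect, pF = 0.3 and w = 0.5. The numerator is 0.3 + 0.7 × 0.5 × 0.9 = 0.615. With q = 0 the ratio is 0.615/0.300 = 2.05. With q = 0.5 it is 0.615/0.4575 = 1.34.
- Smallest effect, pF = 0.8 and w = 8/52. The numerator is 0.8 + 0.2 × 0.1538 × 0.9 = 0.8277. With q = 0 the ratio is 0.8277/0.8000 = 1.03. With q = 0.5 it is 0.8277/0.8138 = 1.02.
- With q = 1 the ratio is 1.00 throughout. With q above 1 the denominator exceeds the numerator and the ratio falls below 1.

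**3. How much the period matters.** Take assumed detection of 0.8 at sessions and 0.4 at follow-up. For events in the session period, BA records 1 − 0.2 × 0.6 = 0.88. Usual care records 0.40 with no sessions, or 0.5 × 0.88 + 0.5 × 0.40 = 0.64 if half have similar sessions. The ratios are 0.88/0.40 = 2.2 and 0.88/0.64 = 1.4. Over the full 12 months with events spread evenly, BA records (8/52) × 0.88 + (44/52) × 0.40 = 0.474. Usual care records 0.40, or (8/52) × 0.64 + (44/52) × 0.40 = 0.437. The ratios shrink to 0.474/0.40 = 1.18 and 0.474/0.437 = 1.08.

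**4. Restricting to events first reported at follow-up.** With the same probabilities, a BA event in the session period reaches this table only if the sessions missed it: 0.2 × 0.4 = 0.08. Usual care gives 0.40 with no sessions, or 0.5 × 0.08 + 0.5 × 0.40 = 0.24 if half have sessions. The ratios are 0.08/0.40 = 0.20 and 0.08/0.24 = 0.33, so the bias reverses.

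**The case against.** The strongest reply is that the direction is not established. Eight sessions is a maximum for BA. Usual care may be CBT or IPT, and its session record carries the same AE field. A reader might infer from the words on no intervention and signposting that the counts are certainly inflated in BA, perhaps 5-fold or 2.2-fold. The documents do not support that. The 5-fold figure sets the BA maximum against a usual-care participant with no sessions. The 2.2 holds only for session-period events under one pair of assumed detection rates. This part of the objection stands in full.

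Second, how AEs are solicited commonly belongs to the protocol, which is not at hand. Elicitation at follow-up is inferred, and so is the idea that those who answer only the Qualtrics questionnaire are never asked. That route applies to both arms, and no imbalance is shown. The categories of the reporter and time-point fields are not given either, and the time point may mean when the event occurred rather than when it was reported. These limits stand and shape the fix. They do not remove the point, because pooling without a split or caveat is fixed by the SAP itself.

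Third, the summary is descriptive, with no test, and sessions attended are reported elsewhere by arm. That limits the harm to interpretation. It does not link contacts to events, so the reader would have to make the connection unaided.

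A reader might also infer that events first reported at the 6- and 12-month contacts form a fair, contact-matched comparison. They do not: sessions come before follow-up, so events already caught at sessions drop out of the more closely observed arm.

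**Conclusion.** The point holds as a risk, not as a demonstrated bias. Events can be recorded at sessions in both arms, session numbers may differ widely, and section 5.9.4 pools the reports without split or caveat. The pooled counts may be biased, probably towards more events in BA if usual care has fewer sessions. Under equal true rates and the assumed ranges above, the recorded ratio is about 1.03 to 2.05 with no usual-care sessions, 1.02 to 1.34 at half the BA coverage, 1.00 at equal coverage, and below 1 if usual care has more. Which case applies depends on sessions actually attended. SAEs may be less affected if they also reach the team by other routes, which the SAP does not settle. This is a cheap improvement to a descriptive summary; the primary analysis is untouched.

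**What to change.** In section 5.9.4, keep the pooled summary and add one table of AEs and SAEs by arm, as follows.

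- Split by reporting route: session record versus follow-up or other, from the reporter and time-point fields as far as their categories allow.
- Split by onset period: session period versus later, from the date of onset. Define the session period as one fixed interval from randomisation for both arms, since a usual-care participant without sessions has no session dates.
- Give the number and percentage of participants with at least one event.
- Show sessions attended and follow-up interviews completed by arm alongside.
- State that pooled and session-reported counts are not like-for-like between arms, and that events with onset after the session period are the more comparable set.
- Do not present events first reported at follow-up as a contact-matched comparison.

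The cost is a few sentences of SAP text and one table from fields already collected. The downside is small counts per cell.

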5.10 Other analyses

5.10.1 Mediation analysis

Mediation analysis (using the *mediate* command in Stata) will be used to examine direct and indirect effects of treatment on the RCADS-25 at 12-months post-randomisation with the indirect effect being mediated through the BADS-SF score at 6-months post-randomisation. The model for the outcome will include trial arm, age, sex, setting and site. In order to account for hidden confounding between the mediation variable and outcome (Emsley R et al (2010)), the model for the mediator will include these terms and in addition interaction terms between trial arm and the following variables: age, sex, setting and site.

This analysis will be repeated with the CDRS-R score at 12-months post-randomisation in place of the RCADS-25 score.

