3.5 Sample Size

The most recent meta-analysis of BA for depression in young people (Martin & Oliver, 2018) reported a large effect size of -0.7 (95% CI -1.20, -0.20). There is no widely accepted minimal important difference (MID) for the RCADS (our primary outcome measure); therefore, we are seeking to obtain an effect size of $d=0.5$, which is accepted (albeit with criticism) as a universal standard for MID (King 2011, Norman et al 2003) and is an effect size which NICE has previously used as a ballpark for the adoption of interventions (NICE, 2014). A sample size of 172 (86 in each group) will have 90% power to detect an effect size of 0.5 on the RCADS using a two-group t-test with a 0.05 two-sided significance level. Assuming an average of 5 participants per therapist, an ICC of 0.01 (DE=1.04) and 23% loss to follow-up (mean of drop-out rates 14-32% from 5 existing RCTs on BA), we will aim to recruit 236 young people (118 in each group).

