3.6 Assessment of Eligibility and Randomisation

Potential individuals eligible for participation in ComBAT will be referred by professionals from schools, charities and CAMHS, or self-referred via posters with a contact for their site and/or embedded links to the ComBAT expression of interest form. Trained research assistants within the ComBAT team will conduct screening of the individuals. This includes completing the RCADS depression subscale, the PHQ-9A and determining eligibility based on prespecified inclusion/exclusion criteria specified within the screening CRF in Section 3.4.3. If the young person scores higher than 14 in the PHQ-9A and/or provides answers to the supplementary risk questions, related to suicidal thoughts or attempts, they will be invited to attend a secondary eligibility assessment conducted by a clinical member of the ComBAT

team to confirm if they are eligible. If an individual was deemed eligible, then a research assistant will contact the young person and their parent/guardian to arrange a time to obtain informed consent/assent and conduct a baseline visit. If the clinician felt that the young person's responses indicated more severe depression and complex risk, they would explain that the trial is not suitable for them and provide signposting for further support. The referring site (if applicable) would be informed of this.

Once informed consent/assent is obtained and baseline visit completed, young people will be randomised in a 1:1 ratio to either BA or usual care using simple randomisation. Randomisation will be implemented using a web-based system designed and developed by the data management team at York Trials Unit (YTU). The allocation sequence will be generated by an independent YTU statistician and embedded using a central, web-based randomisation system at YTU.

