5.7 Primary Analysis

The RCADS-25 will be summarised descriptively at each collected time point by trial arm. Mean scores and confidence intervals will be illustrated graphically.

The primary analysis will be conducted on an intention to treat (ITT) basis, including patients in the groups to which they were randomised.

The primary analysis will compare the continuous RCADS-25 T-score between treatment arms at 6-months post randomisation. This will be analysed using a mixed-effects linear regression model, including all available follow-up time points. The model will adjust for the RCADS-25 at baseline and include as fixed effects: trial arm, arm-by-time interaction, age, sex, setting and site. Random effects will be included to account for the repeated measures within patients and for possible clustering by therapist, patient, and therapist nested within treatment arm.

Adjusted mean differences between treatment groups will be presented at each timepoint with an associated 95% confidence interval (CI) and p-value.

For the modelling of repeated measurements, the best fitting (based on Akaike information criteria (AIC) and Bayesian information criteria (BIC)) covariance pattern that is not significantly different from an unstructured pattern will be selected. The model will provide an overall treatment effect over 6 months as well as estimates at the 12-month time point. These will be reported as mean differences between treatment groups with 95% confidence intervals and associated p-values. The estimate at the 6-month time point will serve as the primary endpoint.

Data will be assumed missing at random. The assumptions of normality and homoscedasticity of residuals will be checked using graphical methods, and if the assumptions are in doubt the data will be transformed prior to analysis or alternative non-parametric analysis methods will be explored.

The primary analysis will be checked by a second statistician before the release of any results.

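### The mediation models leave out the baseline outcome and BADS-SF scores, and their arm-by-covariate interactions do not account for hidden confounding as the SAP says

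*SAP*

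**What the plan says.** SAP section 5.10.1 plans a mediation analysis with Stata's *mediate* command. The outcome is RCADS-25 at 12 months and the mediator is BADS-SF at 6 months; the analysis is then repeated with CDRS-R at 12 months as the outcome. The covariates are enumerated: "The model for the outcome will include trial arm, age, sex, setting and site". The mediator model has the same terms plus interactions of arm with age, sex, setting and site. The stated reason for the interactions is: "In order to account for hidden confounding between the mediation variable and outcome". A methods paper on mediation is cited, but the section names no instruments, two-stage fit, correlated residuals or sensitivity analysis for mediator-outcome confounding.

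Elsewhere the SAP adjusts for baseline. Of the primary model, section 5.7 says: "The model will adjust for the RCADS-25 at baseline". Sections 5.9.2 and 5.9.3 replace that term with baseline CDRS-R and baseline BADS-SF for those outcomes. Sections 3.4.1 and 3.4.2 confirm that all three scales are collected at baseline.

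**The concern.** Randomisation protects the comparison of arms. It does not protect the association between 6-month BADS-SF and 12-month symptoms, because 6-month BADS-SF is not randomised. A young person who starts more depressed and less active is likely to be less active at 6 months and more depressed at 12 months, whether or not activation causes anything. Baseline symptom score and baseline BADS-SF are thus the obvious measured confounders, and the listed models contain neither.

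The interactions do not fill the gap. In a two-regression decomposition the indirect effect is the arm's shift in the mediator multiplied by the mediator's coefficient in the outcome model. The interactions enter only the first factor; the confounding is in the second. The report could therefore present an indirect effect through activation where none exists and also state that hidden confounding had been accounted for.

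**Working it through.** **Sample size used.** Section 5.10.1 gives no figure of its own, so the trial's planned size is the starting point. Section 3.5 states: "A sample size of 172 (86 in each group) will have 90% power to detect an effect size of 0.5 on the RCADS". The two-sample t-test gives 85.03 per arm, so 86 per arm, or 172. The inflation inputs are: "Assuming an average of 5 participants per therapist, an ICC of 0.01 (DE=1.04) and 23% loss to follow-up". Then 172 × 1.04 = 178.88 and 178.88 / 0.77 = 232.3, so 233 against the stated 236: close enough to count as reproduced. Participants with follow-up: 236 × 0.77 = 181.7, about 182.

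**Assumed inputs (not in the SAP), in SD units.**
- a, arm effect on 6-month BADS-SF: 0, 0.3, 0.5.
- ρ, correlation of baseline RCADS-25 with baseline BADS-SF: 0, -0.3, -0.5, -0.6.
- s, coefficient from each baseline score to its own follow-up: 0.4, 0.5, 0.7.
- True effect of 6-month BADS-SF on 12-month RCADS-25: zero.

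**Formula.** With unit variances, the covariance of mediator and outcome given arm is s²ρ when the baselines are left out. The mediator coefficient is then b = s²ρ instead of 0, and the spurious indirect effect is a·s²·ρ. For example, 0.5 × 0.5² × (-0.5) = -0.0625.

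**Simulation at n = 182.** There were 1,500 replicates. Mediator and outcome regressions were fitted separately, with an arm-by-mediator term allowed in the outcome model. A false positive means that both a and b are significant. Results at a = 0.5:

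| ρ | s | a·s²·ρ | SAP models | SAP models without interactions | SAP models plus baselines | False positives, SAP | False positives, with baselines |
|---|---|---|---|---|---|---|---|
| 0 | 0.5 | 0 | -0.001 | -0.001 | 0.000 | 4.3% | 5.1% |
| -0.3 | 0.4 | -0.024 | -0.022 | -0.022 | 0.001 | 5.5% | 4.4% |
| -0.5 | 0.5 | -0.0625 | -0.062 | -0.062 | -0.001 | 20.6% | 4.8% |
| -0.6 | 0.7 | -0.147 | -0.147 | -0.147 | 0.003 | 75.1% | 6.6% |

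Monte Carlo error near 5% is about √(0.05 × 0.95 / 1500) = 0.6 percentage points, so the gap in the second row is small.

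At a = 0.3 the three correlated scenarios give -0.013, -0.040 and -0.089 with the SAP models; with baselines all are within 0.001 of zero. At a = 0 the spurious effect is zero throughout. Higher RCADS-25 is worse, so a negative indirect effect reads as benefit through activation.

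**What the interactions do.** Removing them left the mean indirect effect unchanged to three decimals in every scenario. A further run (a = 0.5, ρ = -0.5, s = 0.5) added an unmeasured confounder with loading 0.4 and a real arm-by-age interaction of 0.3 SD on the mediator:
- SAP models, with or without the interactions: -0.136 SD.
- Baselines added: -0.101 SD.
- Same data model at n = 400,000, mediator coefficient (truth 0): -0.281 by ordinary regression, and 0.006 by two-stage least squares with the interactions as excluded instruments.

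**The case against.** The strongest reply is that leaving the interactions out of the outcome model is exactly the exclusion structure of an instrumental-variable analysis, so an IV fit was probably intended and the defect is only the choice of command. Under a valid IV fit, omitting the baselines would cost precision more than validity. That may be the intention, but it is not what is written. Section 5.8.1 shows that the SAP spells out an IV model and names its instrument when it wants one; section 5.10.1 names only *mediate* with one outcome model and one mediator model.

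The second reply is about size, and much of it stands. A reader might infer that a spurious mediated effect is to be expected. The SAP does not support that: it gives none of the correlations, and the effect vanishes if BA does not shift BADS-SF or if the baseline scales are uncorrelated. The entry rule of at least 65 on the RCADS depression subscale (section 3.4.3) restricts the range of baseline severity and would tend to weaken the correlations that drive the bias. The 75% figure needs all three assumed inputs at their extremes.

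A reader might also infer that adding the baselines cures the confounding. The near-zero results in the table hold because baseline is the only confounder simulated there; with an unmeasured one, -0.136 fell only to -0.101.

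Finally, the analysis is listed under other analyses and has no table template in section 8.1.

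**Conclusion.** The point holds in conditional form. Both mediation models omit measured, plausible confounders that the SAP's other outcome models use, and the hidden-confounding claim is not supported by the models described. Following the section as written can produce a spurious indirect effect in the direction of mediation, provided that BA raises 6-month BADS-SF and that baseline scores are negatively correlated and persist. Its size is about 0 to -0.15 SD over the assumed ranges; the true place in that range cannot be fixed from the SAP. No conversion to T-score points is offered, because the SAP gives no SD for this selected sample. The primary and secondary treatment comparisons are untouched, so this is a correction that should be made to a supporting analysis, not a threat to the trial's main conclusion.

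**What to change.** Add the baseline outcome score (RCADS-25, or CDRS-R in the repeat) and baseline BADS-SF to both the outcome and the mediator model, and state that this removes measured baseline confounding only.

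Then choose one of two courses:
- Delete the statement that the interactions account for hidden confounding.
- Keep the aim and specify a separate two-stage least squares sensitivity analysis, with the arm-by-covariate terms as excluded instruments for 6-month BADS-SF, and report first-stage strength. It should state the assumption that these interactions affect the outcome only through BADS-SF. That assumption needs defending, since section 5.8.4 anticipates that the effect on RCADS-25 may differ by age, gender and setting.

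The cost is SAP wording and code; the data are already part of the planned collection. The drawback of the second course is likely imprecision at about 182 participants, which is why it should stay a sensitivity analysis.
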